**Figure 6 Summary of Covariate Ascertainment in Cohort Analyses**

a Earliest end date of study period, enrolment termination date, death, vaccination with any COVID-19 vaccine other than the vaccine granting access to the cohort, also for each specific AESI: date of the AESI, end of risk window for that specific AESI.

Note that information on inclusion, exclusion, and covariate assessment windows will all be available before the index date in each data source, except when an alternative look-back-specific risk window is specified. For comedications and healthcare utilisation, this time window will be 183 days before the index date, except if a different time window is specified for specific medications or healthcare utilisation measures.

AESI, adverse event of special interest; COVID-19, coronavirus disease 2019.

Source: Original design diagram template can be found at [www.repeatinitiative.org/projects.html](http://www.repeatinitiative.org/projects.html).

## 9.4 Data Sources

This study will use data from existing secondary automated electronic health data sources that are population based and can provide high quality data on COVID-19 vaccines (ie, product type and dates), outcomes (ie, diagnoses, procedures, and treatments), and important covariates (eg, clinical characteristics, demographics). Data sources have also been selected based on the ability to provide periodic updates during the study period.

The 5 research partners at the proposed collaborating institutions with access to the data in each of the proposed countries have indicated their interest in participating in the study and have reviewed the study protocol. It also may be possible to increase the study size in the UK by extending the study beyond practices included in the CPRD. Additional linked electronic health data may be available through the OpenSAFELY programme ([Grint et al 2021](#), [NHS Digital 2020](#), [Wong et al 2021](#)). This data source may be proposed as exploratory.

#### **9.4.1 CPRD, United Kingdom**

The CPRD collates the computerised medical records of a network of GPs in the UK who act as the gatekeepers of healthcare and maintain subjects' life-long electronic health records. The data are sourced from over 2,000 primary care practices and include 50 million patients, of whom 16 million are currently registered and active (<https://cprd.com/Data>, accessed 1 March 2021). General practitioners act as the first point of contact for any non-emergency health-related issues, which may then be managed within primary care and/or referred to secondary care, as necessary. Secondary care teams also provide feedback information to GPs about their patients, including key diagnoses. The data in the CPRD are updated monthly and include demographic information, prescription details, clinical events, preventive care, specialist referrals, hospital admissions, and major outcomes, including death ([Herrett et al 2015](#), [Wolf et al 2019](#)). Most of the data are coded using Read or SNOMED codes. Data validation with original records (specialist letters) is available.

Depending on the type of electronic medical software used by the general practice, data are collected into either the CPRD GOLD (General Practitioner Online Database) or the CPRD Aurum database. Data include demographics, all GP/healthcare professional consultations, diagnoses and symptoms, results from laboratory tests, information about treatments (including prescriptions), data on referrals to other care providers, hospital discharge summaries (date and Read/SNOMED codes), hospital clinic summaries, preventive treatment and immunisations, and death (date and cause). Lag time for CPRD Aurum is usually 1 month, although this may be extended due to CPRD database technical updates. Information about vaccinations from mass vaccination campaigns during the pandemic is expected to transfer to GPs and into the subject's medical records (via National Health Service [NHS] systems rather than subjects informing the GP); however, the lag time for this transfer is not yet clear.

Linkage of the CPRD primary care data with other subject-level datasets is available for English practices that have consented to participate in the linkage scheme. In more than 80% of the CPRD panel practices, the GPs have agreed to permit the CPRD to link at the subject level to these subject-level datasets. The Hospital Episode Statistics (HES) database contains details of all admissions to NHS hospitals in England (Accident and Emergency, Admitted Subject Care, and Outpatient); approximately 46.8 million individuals in the CPRD are linked to the HES database. Not all subjects in the CPRD have linked data (eg, if they live outside

England, if their GP has not agreed that their data may be used in this way). As with standard CPRD subjects, HES data are limited to subjects with research-standard data. The CPRD records are linked to the HES using a combination of the subject's NHS number, sex, and date of birth ([Williams et al 2012](#)). Additional CPRD-linked datasets include Death Registration data from the Office for National Statistics, which includes information on the official date and causes of death (using International Classification of Diseases codes). The Pregnancy Register will be used to identify pregnant women at the index date.

In addition, other CPRD-linked COVID-19 datasets, which may provide further follow-up information on AESIs, include the Public Health England (PHE) Second Generation Surveillance System (SGSS) COVID-19–positive virology test data, PHE COVID-19 Hospitalisation in England Surveillance System (CHESS), and the Intensive Care National Audit and Research Centre (ICNARC) data on COVID-19–related intensive care admissions.

Linked datasets are usually updated every 6 months, and the lag time between data recording and data availability varies by dataset. The latest linkage set (set 22) contains an update of priority linkages to support COVID-19 research, along with the CPRD-linked SGSS COVID-19–positive virology test data and CHESS hospitalisation and intensive care unit/high dependency unit data up to the end of March 2021.

The present study included active CPRD Aurum practices. These practices include an estimated 13.3 million current subjects. CPRD is listed under the European Network of Centres for Pharmacoepidemiology and Pharmacovigilance (ENCePP) resources database, and access was provided by the Drug Safety Research Unit (DSRU).

#### **9.4.2 VID, Spain**

The VID is a set of population-wide electronic databases covering residents of the Valencia region in Spain, representing approximately 5 million individuals ([Garcia-Sempere et al 2020](#)). All the information in the VID databases can be linked at the individual level through a single personal identification. The data sets in the VID are as follows:

- The Population Information System (SIP) is a database that provides basic information on health system coverage (eg, dates and causes of Valencia health system entitlement or disenitment, insurance modality, pharmaceutical copayment status, assigned healthcare department) as well as some sociodemographic data (eg, sex, date of birth, nationality, employment status, geographic location). Importantly, the SIP database includes the date of death captured from the Mortality Registry. The SIP database is paramount to the VID, as it is the source of the individual, exclusive, and permanent identifier number associated with each individual (the SIP number), which is then used throughout the rest of the databases, thereby allowing data linkage across the multiple databases in the network.
- The Ambulatory Medical Record (ABUCASIS) is the electronic medical record for primary and specialised outpatient activity, with 96% population coverage since 2009. ABUCASIS is integrated by 2 main modules: the Ambulatory Information System (SIA)

and the Pharmaceutical Module (GAIA), including paediatric and adult primary care, mental healthcare, prenatal care, and specialist outpatient services, as well as providing information about dates, visits, procedures, laboratory test results, diagnoses, and clinical and lifestyle information. It also includes information on several health programmes (eg, healthy children, vaccines, pregnancy, notifiable diseases), the primary care nurse clinical record, and the health-related social assistance record. The SIA module uses the International Classification of Diseases, 9th Revision, Clinical Modification (ICD-9-CM) for coding diagnoses (and, partially, the International Classification of Diseases, 10th Revision, Spanish Edition [ICD-10-ES] from 2019). The SIA also uses the Clinical Risk Groups system to stratify the morbidity of the entire population.

- The GAIA Pharmaceutical module stores data on all outpatient pharmaceutical prescriptions and dispensings, including both primary care and outpatient hospital departments, using the Anatomical Therapeutic Chemical (ATC) classification system and the National Pharmaceutical Catalogue, which allow the identification of the exact content of each dispensing. GAIA does not include in-hospital medication or medication administered in the Accident and Emergency Department (AED). GAIA provides detailed information on prescriptions issued by physicians, such as the duration of treatment and dosage.
- The Hospital Medical Record (ORION) provides comprehensive information covering all areas of specialised care, from admission, outpatient consultations, hospitalisation, emergencies, diagnostic services (eg, laboratory tests, imaging, microbiology, pathology), pharmacy, surgical block including day surgery, critical care, prevention and safety, social work, at-home hospitalisation, and day hospitalisation. ORION is currently in the process of being integrated for the whole region, with several databases already fully integrated and available for all hospitals, including the Minimum Basic Data Set at Hospital Discharge (MBDS) and the AED clinical record.
- The MBDS is a synopsis of clinical and administrative information on all hospital admissions and major ambulatory surgery in the Valencia health system hospitals, including public-private partnership hospitals (approximately 450,000 admissions per year in the region). The MBDS includes admission and discharge dates, age, sex, geographic area and zone of residence, main diagnosis at discharge, up to 30 secondary diagnoses (comorbidities or complications), clinical procedures performed during the hospital episode, and the diagnosis-related group(s) assigned at discharge. The MBDS used the ICD-9-CM system for coding through December 2015 and ICD-10-ES afterward. The MBDS was extended in 2015 to include the “present on admission” diagnosis marker and information on tumour morphology.
- The AED clinical record was launched in 2008 and collects triage data, diagnoses, tests, and procedures performed in public emergency departments. As with the MBDS, the coding system used the ICD-9-CM until December 2015 and the ICD-10-ES thereafter. Diagnosis codification has been increasing from approximately 45% of all emergency department visits between 2008 and 2014 up to approximately 75% in 2017, largely due to the progressive incorporation of hospital coding.

Data on vaccine exposure may be obtained from the Vaccine Information System (VIS), which includes information on vaccine type, manufacturer, number of doses, location and administration date, adverse reactions related to vaccines, and if applicable, risk groups. Information in the VIS is updated daily.

All databases included in the VID are updated frequently (every 1 to 3 months), except the MBDS database, which is updated every 6 months.

Information on pregnancy and pregnancy outcomes is available in the VID database, although some end dates of pregnancy may be missing. However, the mother-baby linkage is not available.

### **9.4.3 SIDIAP, Spain**

The Information System for Research in Primary Care (SIDIAP) in Catalonia, Spain, is a primary care database set up by the Institute of Research in Primary Care (IDIAP Jordi Gol) and Catalan Institute of Health (Institut Català de la Salut). The database collects information from 278 primary healthcare centres and includes more than 5.8 million patients (approximately 78% of the Catalan population) covered by the Catalan Institute of Health and is highly representative of the Catalan population ([Willame et al 2021](#)).

The SIDIAP data comprise the clinical and referral events registered by primary care health professionals (ie, GPs, paediatricians, and nurses) and administrative staff in electronic medical records, comprehensive demographic information, community pharmacy invoicing data, specialist referrals, and primary care laboratory test results. The SIDIAP can also be linked to other data sources, such as the hospital discharge database, on a project-by-project basis. Health professionals gather this information using International Classification of Diseases, 10th Revision (ICD-10) codes, ATC codes, and structured forms designed for the collection of variables relevant to primary care clinical management, such as country of origin, sex, age, height, weight, BMI, tobacco and alcohol use, blood pressure measurements, and blood urine test results. In relation to vaccines, information on all routine childhood and adult immunisations is included in addition to the antigen and the number of administered doses.

Currently, because of the COVID-19 pandemic, having shorter-term updates to monitor the evolution of the pandemic is a possibility. Recent reports have shown the SIDIAP data to be useful for epidemiological research. SIDIAP is listed under the ENCePP resources database ([www.encepp.eu/encepp/resourcesDatabase.jsp](http://www.encepp.eu/encepp/resourcesDatabase.jsp)). The SIDIAP database was characterised in the ADVANCE project and considered fit for purpose for vaccine coverage, benefits, and risk assessment (<http://www.encepp.eu/encepp/viewResource.htm?id=4646>).

Information on pregnancy, pregnancy outcomes, and mother-baby linkage is available in the SIDIAP database.

#### **9.4.4 ARS Toscana, Italy**

The ARS Toscana is a research institute of the Tuscan regional government. Tuscany is an Italian region with approximately 3.6 million inhabitants. The ARS database comprises all the data that are collected in Tuscany related to healthcare delivered to those who are official residents of the region. Additionally, ARS collects data tables from regional initiatives.

The ARS database routinely collects primary care and secondary care prescriptions of drugs for outpatient use and is able to link them at the individual level with hospital admissions, admissions to emergency care, records of exemptions from copayment, dispensings of diagnostic tests and procedures, causes of death, and a pathology registry, which has been available for the last few years and includes complete information only for morphology and topography. Occasionally, ARS may request retrieval of information from medical records or laboratory results regarding specific subpopulations and link this information to its core data.

Patients in ARS can be characterised in terms of age, sex, comorbidities (via algorithms), socioeconomic indicators, medication taken regularly on an outpatient basis, date of death, and healthcare utilisation (including visits to specialists, visits to ambulatory cancer care units, and visits to an emergency department or urgent care centre). Cause of death is available with a lag time of 3 years.

The lag time from a healthcare encounter to incorporation of data for research purposes is approximately 3 to 4 months. All patients in the ARS database can be linked to mortality data through deterministic linkage. There is no restriction on reporting small numbers.

Participation of the ARS database in a research study includes mandatory compliance with the ENCePP Code of Conduct ([ENCePP 2018b](#)). The ENCePP Code of Conduct “provides a set of rules and principles for pharmacoepidemiology and pharmacovigilance studies to promote scientific independence and transparency throughout the research process.”

Information on pregnancy, pregnancy outcomes, and mother-baby linkage is available in the ARS Toscana database.

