**Table 2 Study Milestones**

Milestone	Planned date a	Actual/revised date
Protocol submission	01 Apr 2021	01 Apr 2021
Protocol endorsement by EMA/MHRA	TBD (expected Jul 2021)	Version 3.0: 9 Jul 2021 (MHRA); 22 Jul 2021 (EMA)
Registration in the EU PAS Register	No later than 6 months after EMA protocol endorsement and before start of data collection	Registered 7 Oct 2021 (EUPAS43556)
Statistical analysis plan submission	4 months after protocol endorsement (expected Nov 2021)	Version 1.0, 22 Nov 2021
Start of data collection b	4 months after protocol endorsement (expected Nov 2021-first interim analysis)	18 Feb 2022
End of data collection c	20-21 months after protocol endorsement (expected Mar/Apr 2023 - final report)	30-31 months after endorsement of protocol revised version 3.0 (expected Oct-Dec 2023 - final report)
Progress Report 1	3 months after protocol endorsement (expected Oct 2021)	22 Oct 2021
Interim Report 1	9 months after protocol endorsement (expected Apr 2022)	22 Apr 2022

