### Historical Comparators Cohort

A potential comparator subject (**historical comparators**) identified during the period between 2017 and 2018 will be eligible to be matched from the date the subject met all the following inclusion criteria:

- Had at least 12 months of prior data available.

The **index date** for the historical comparators will be same day and month of the AZD1222 index date minus 3 years (subjects from 2018) or 4 years (subjects from 2017)—an approach that intends to address seasonality.

Subjects will be **matched** to AZD1222-vaccinated subjects on age ( $\pm 2$  years), sex, region, and status according to the 5 special populations. Matching will be done with replacement at a ratio of 1:1.

Whether all potential comparators, or only a sample, will be included in the selection of the comparator cohorts will depend on the data governance rules and data management capabilities of each research partner, which is still to be determined. The SAP will document this decision, along with other details about matching criteria.

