### 9.2.2 Study Period

The study period will start on the date AZD1222 vaccination began in each country. The first vaccinations started approximately 1 week after approval date, which was 30 December 2020 in the UK and 29 January 2021 in the EU. The study period duration will be 24 months in each data source or until latest data available at the time of start of data collection (data extraction), ie, this duration may include a few more months in the data sources where the lag time to obtain the data is shorter.

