### **9.7.12 Progress and Interim Analysis**

A first progress report was submitted to the regulatory agencies to update the status of the data source participation being explored at the time of the protocol endorsement, to confirm that data extractions and analysis as well as other study activities are being conducted as planned, and to discuss the impact of the changes in the uptake of the vaccine on the study and whether the inclusion of other databases should be explored. The second progress report, which replaced interim report 3, as agreed with EMA, will be delivered in April 2023, followed by the feasibility assessment report for the comparative analysis in June 2023.

Interim reports will include information from the study period available at the time of each data extraction, a description of the number of subjects vaccinated with 1 or 2 doses of AZD1222, the number of subjects vaccinated with one dose of AZD1222 and a second dose of another COVID-19 vaccine, IRs of the AESI, and comparative analyses (when the data have been accrued in the database and are available to support those analyses with sufficient precision).

The study periods to be included in each interim report will depend on the database, linkages, lag times, and the time required to obtain the data by the research institutions. In addition, for the first interim report, study period will also depend on time needed to allow for protocol endorsement by the EMA, contracting between research institutions, a minimum set of analytical instructions (or the whole SAP), data extraction, analysis, and reporting. For AESIs that require linkage with other databases such as hospital database or cause of death registers, time lags may be longer and may not be included in the first interim report.

Descriptions of the cohorts and estimations of IRs and any other measures will be performed as described in Section 9.7.

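### In ARS Toscana cause of death lags 3 years, so at final extraction it is complete for historical comparators and absent for essentially all AZD1222 vaccinees; any outcome algorithm that uses it makes that comparison unequal

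*Protocol*

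**What the plan says.** - **Lag.** Protocol 9.4.4 on ARS Toscana: "Cause of death is available with a lag time of 3 years". The same section lists date of death, hospital and emergency admissions and linkage to mortality data, and puts the general lag for healthcare encounters at about 3 to 4 months.
- **Final extraction.** Table 2 gives the revised end of data collection as "30-31 months after endorsement of protocol revised version 3.0 (expected Oct-Dec 2023 - final report"). The endorsement dates in that table are 9 July 2021 (MHRA) and 22 July 2021 (EMA).
- **Start of vaccination.** Section 9.2.2 places first use about a week after approval, "which was 30 December 2020 in the UK and 29 January 2021 in the EU".
- **Historical comparators.** Section 9.2.1.1.3 sets their index date from the "AZD1222 index date minus 3 years (subjects from 2018) or 4 years (subjects from 2017"). Section 9.2.3.1 ends their follow-up on 31 October 2019.
- **Outcome.** Sudden death has a risk interval of days 0-6 (Table 3). Section 9.7.7 compares it with historical comparators by prevalence proportion ratio and difference.
- **Acknowledgement of lag.** Section 9.7.12 says: "For AESIs that require linkage with other databases such as hospital database or cause of death registers, time lags may be longer". The only consequence it draws is possible omission from the first interim report.

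**The concern.** Version 4.0 added a comparator from 2017-2018 to a vaccinated cohort from 2021 onwards. A data bank with a 3-year lag can then be full for one arm and empty for the other, purely by calendar.

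Section 9.9.1 discusses the non-comparability of historical subjects in terms of changed background rates, access to care and care-seeking. It does not mention unequal availability of an outcome data bank. Section 9.7.5 generally treats absence of information on clinical events as absence of the event. Under that rule, a cause of death that has not yet arrived could be counted as a non-event.

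At stake is a source-specific sudden-death ratio in a safety study that could differ from 1 because of register timing alone.

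**Working it through.** **Step 1: the milestone.** The superseded plan reproduces: July 2021 + 20-21 months = March/April 2023, as Table 2 states. The revised entry does not:

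- 22 July 2021 + 30-31 months = 22 January to 22 February 2024 (from 9 July 2021: 9 January to 9 February 2024).
- October to December 2023 is 27 to 29 months after endorsement.

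Both readings are carried forward.

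**Step 2: reach of cause of death in ARS.** Formula: extraction date minus 3 years, compared with first EU use at about 29 January 2021 + 7 days = 5 February 2021.

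| Extraction | Cause of death complete to | Relative to 5 Feb 2021 |
|---|---|---|
| 1 Oct 2023 | 1 Oct 2020 | 127 days before |
| 31 Dec 2023 | 31 Dec 2020 | 36 days before |
| 22 Jan 2024 | 22 Jan 2021 | 14 days before |
| 22 Feb 2024 | 22 Feb 2021 | 17 days after |

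On the stated calendar dates no ARS vaccinee is covered. On the latest 30-31 month reading, at most about the first 17 days of roll-out are covered.

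**Step 3: historical comparators.** The latest first-dose window ends on 31 December 2018 + 6 days = 6 January 2019, so its cause of death is available by 6 January 2022. All historical follow-up ends by 31 October 2019 and is available by 31 October 2022. Coverage is complete on either reading.

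**Step 4: effect on the ARS ratio.** Observed ratio = true ratio x (capture in AZD1222 / capture in historical). The true ratio is set to 1. The shares below are assumptions, because the protocol gives none.

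| How the ARS algorithm uses cause of death | Formula | Results |
|---|---|---|
| A share s of cases is found only through the register | 1-s | s = 0, 0.25, 0.5, 1 gives 1, 0.75, 0.5, 0 |
| A share e of deaths is removed as explained, possible in historical subjects only | 1/(1-e) | e = 0.25, 0.5, 0.75 gives 1.33, 2, 4 |
| Not used (date of death or encounter codes only) | 1 | 1 |

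**Step 5: weight of ARS.** From Table 4, ARS has 336,889 of 5,557,094 matched vaccinees (6.1%), or 343,478 of 5,964,519 vaccinees (5.8%). Assume equal background risk and no bias in the other four sources. The crude pooled ratio is then (1-0.061) + 0.061 x (ARS ratio):

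- With an ARS ratio of 0: about 0.94, the lowest value possible.
- With an ARS ratio of 2: 0.939 + 0.121 = about 1.06.

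This is only an illustration. The protocol pools source-specific estimates, so the actual weight of ARS would differ.

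**The case against.** The strongest reply is that nothing in the protocol says sudden death is identified from cause of death. Section 9.3.2 describes algorithms built on diagnosis, procedure and treatment codes and leaves the detail to the SAP. It also aims for uniform definitions across sources, and VID and PHARMO are described as holding date of death or mortality rather than cause. A uniform definition might therefore avoid cause of death. Section 9.6.2, however, lets algorithms differ by database. This reply stands in part: bias is conditional on the algorithm, and leaving the algorithm to the SAP is not itself a fault.

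A reader might infer that ARS will show a false protective effect. The documents do not support that, since step 4 allows a ratio that is too low, too high or unaffected. Nor do they show that ARS adds no information against concurrent unvaccinated comparators, or that other AESIs shift in the same direction. Concurrent and active comparators share the gap with the vaccinees, so the timing does not create unequal capture there.

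A second reply is that 9.7.11 makes pooling depend on a review that includes the type and availability of data. That review looks across sources. It does not stop a within-source estimate with unequal capture between arms from being reported, and each source is reported separately in any case. By contrast, 9.7.10 makes the role of CPRD hospital data depend on its lag at the final analysis; ARS cause of death has no similar provision.

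Third, 9.7.12 concerns interim reports and does not claim that the lag is resolved later. That is fair, but no other section takes up the lag for the final report.

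**Conclusion.** The point holds in conditional form. The timing is established from the protocol's own dates: for the historical comparison in ARS Toscana, cause of death is complete in one arm and essentially absent in the other. This takes the lag as exactly 3 years and first use in Tuscany as about a week after EU approval.

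Whether this biases the estimate, and in which direction, depends on whether and how the ARS algorithm uses cause of death. The protocol neither fixes this nor lists the problem as a limitation.

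The scope is small: exploratory objective 2, one of five sources, about 6% of vaccinees. The pooled effect is likely to be modest, but the ARS-specific ratio could be badly wrong. This is a cheap improvement and does not threaten the primary objectives.

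**What to change.** In 9.7.7, state that within each data source the AZD1222-historical comparison uses only outcome data banks that are complete for both calendar periods at extraction. For ARS Toscana, either use no cause-of-death records in either cohort for this comparison, or omit the ARS sudden-death estimate from it and from the pooled result (9.7.11). This works whichever way the bias would run.

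Add unequal data-bank availability to the limitations of historical comparators in 9.9.1. Reconcile the two wordings of the end of data collection in Table 2.

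The cost is a sentence or two and one filter in the extraction. The downside is fewer ARS events, or one source fewer, for this one exploratory comparison.
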